## **10.2 Response Evaluation**

### **10.2.1 Prostate Specific Antigen (PSA)**

- Will be obtained every 3 months for the first 2 years, then as indicated at the discretion of the treating physician.
- Biochemical failure defined as nadir + 2 ng/ml
- Repeat imaging including abdominopelvic CT scan, MRI, or bone scan as clinically indicated.

## **10.3 Toxicity**

**10.3.1** The patient will fill out the American Urological Association (AUA) Symptom Score Sheet and Expanded Prostate Cancer Index Composite (EPIC) questionnaire for gastrointestinal, urinary and sexual quality of life. (14) (Appendix IV and Appendix V, respectively)

**10.3.2** The investigator will report and record all serious adverse events that occur. Adverse events should be reported using the CTC grading system (Appendix III).

**10.3.2** Examples of anticipated acute adverse events include:

- General malaise
- Urinary irritative or obstructive symptoms – dysuria, increased urinary frequency, nocturia, weak stream, hesitancy, and possible urinary retention
- Rectal irritation – loose stools, cramping, straining, hemorrhoidal inflammation
- Radiation dermatitis – dryness, tanning, redness, itching
- Localized hair loss
- Musculoskeletal pain

**10.3.3** Examples of anticipated late adverse events include:

- Bleeding, ulceration and/or perforation of the bladder, rectum, or small bowel
- Neurologic changes including motor weakness, numbness, paresthesias, and/or bowel or bladder dysfunction
- Persistent changes in bowel or bladder habits
- Small bowel obstruction
- Urethral stricture resulting in urinary retention
- Localized skin fibrosis, edema, and/or ulceration
- Erectile dysfunction
- Radiation-induced secondary malignancy

**10.3.4** Reporting of unanticipated or serious adverse events will be reported according to the institutions IRB policy. An unanticipated adverse event is defined as follows:

Any serious adverse effect on health or safety or any life-threatening problem or death caused by, or associated with, stereotactic body radiotherapy, if that effect, problem, or death was not previously identified in nature, severity, or degree of incidence in the investigational plan or application (including a supplementary plan or application), or

any other unanticipated serious problem associated with a treatment that relates to the rights, safety, or welfare of subjects.

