## **2.0 Objectives**

This study will evaluate the local control rate as well as acute and late toxicity rates of stereotactic body radiotherapy (SBRT) for the treatment of organ confined prostate cancer.

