### **2.3 End Points**

- 2.3.1 Primary endpoints will be biochemical control rate
  - Serial blood tests for prostate specific antigen (PSA) levels will be obtained at regular intervals
  - The "Phoenix definition" for biochemical recurrence (nadir + 2 ng/ml) will be used
- 2.3.2 Secondary endpoint will be late toxicity rate.
  - Grading of acute and late complications is defined in Section 12.3 (Appendix III)

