Urinary frequency/urgency	Increase in frequency or nocturia up to 2 x normal; enuresis	Increase >2 x normal but <hourly	≥1 x/hr; urgency; catheter indicated	-	-
Urinary retention	Hesitancy or dribbling, no significant residual urine; retention occurring during the immediate postoperative period	Hesitancy requiring medication; or operative bladder atony requiring indwelling catheter beyond immediate postoperative period but for <6 weeks	More than daily catheterization indicated; urological intervention indicated (e.g., TURP, suprapubic tube, urethrotomy)	Life-threatening consequences; organ failure (e.g., bladder rupture); operative intervention requiring organ resection indicated	Death
Stricture, GU	Asymptomatic, radiographic or endoscopic findings only	Symptomatic but no hydronephrosis, sepsis or renal dysfunction; dilation or endoscopic repair or stent placement indicated	Symptomatic and altered organ function (e.g., sepsis or hydronephrosis, or renal dysfunction); operative intervention indicated	Life-threatening consequences; organ failure or operative intervention requiring organ resection indicated	Death
MUSCULOSKELETAL					
Fracture	Asymptomatic, radiographic findings only	Symptomatic but non-displaced; immobilization indicated	Symptomatic and displaced; operative intervention indicated	Disabling	Death
METABOLIC					
Albumin	3-4 g/dL	2-2.99 g/dL	< 2 g/dL		Death
Alkaline phosphatase	> nl – 2.5 x nl	> 2.5 – 5 x nl	> 5 – 20 x nl	> 20 x nl	-
ALT	> nl – 2.5 x nl	> 2.5 – 5 x nl	> 5 – 20 x nl	> 20 x nl	-
AST	> nl – 2.5 x nl	> 2.5 – 5 x nl	> 5 – 20 x nl	> 20 x nl	-
Bilirubin	> nl – 1.5 x nl	> 1.5 – 3 x nl	> 3 – 10 x nl	> 10 x nl	-
Creatinine	> nl – 1.5 x nl	> 1.5 – 3 x nl	> 3 – 6 x nl	> 6 x nl	Death
SECONDARY MALIGNANCY	-	-	Non-life-threatening basal or squamous cell carcinoma of the skin	Solid tumor, leukemia, or lymphoma	Death

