**13.8 Appendix VIII**

**FOLLOW-UP VISIT FORM – Page 1 of 2**

1. Name \_\_\_\_\_ (last) \_\_\_\_\_ (first)

2. RT Number \_\_\_\_\_

3. Date of Visit: \_\_\_\_ / \_\_\_\_ / \_\_\_\_\_

4. Blood work:

Lab		Date:	Date:	Date:
Total Bilirubin				
Albumin				
Alkaline Phosphatase				
ALT	AST			
PT	PTT			
Creatinine				

4. Radiation Therapy related adverse events

Adverse Event	CTC V3.0 Grade	Timing	Treatment	Comments
ACUTE				
 Fatigue				
 Weight loss				
 Diarrhea				
 Urinary frequency/urgency				
 Dysuria				
 Alopecia				
 Radiation dermatitis				
 Musculoskeletal Pain				
 Neuropathy, Motor				
 Neuropathy, Sensory				
LATE				
 GI Bleeding				
 GI Ulceration				
 GI Perforation				
 GI Stricture				
 Fistula				
 GU Bleeding				
 GU Ulceration				
 GU Perforation				

 GU Stricture				
 Sterility				
 Impotence				
 Pelvic bone injury				
 Neuropathy, Motor				
 Neuropathy, Sensory				

5. Serious adverse event?  No  Yes, submit report to HIC

6. Has systemic therapy been given?  No  Yes

If yes, list therapy

Agent(s)	Start Date	Stop Date
_____	____/____/____	____/____/____
_____	____/____/____	____/____/____
_____	____/____/____	____/____/____

7. PSA since last follow-up visit  No  Yes, date \_\_\_\_/\_\_\_\_/\_\_\_\_

Current Level \_\_\_\_\_ ng/ml

Nadir Level \_\_\_\_\_ ng/ml

8. Radiologic Imaging since last follow-up visit  No  Yes, date \_\_\_\_/\_\_\_\_/\_\_\_\_

CT Scan Date \_\_\_\_/\_\_\_\_/\_\_\_\_

Bone Scan Date \_\_\_\_/\_\_\_\_/\_\_\_\_

9. Disease Status

No evidence of tumor

Biochemical recurrence

Date \_\_\_\_/\_\_\_\_/\_\_\_\_

Local recurrence within the treatment volume

Date \_\_\_\_/\_\_\_\_/\_\_\_\_

Distant recurrence, specify site \_\_\_\_\_

Date \_\_\_\_/\_\_\_\_/\_\_\_\_

10. Additional treatment for recurrent disease

Surgery

Yes  No

Date of surgery \_\_\_\_/\_\_\_\_/\_\_\_\_

Hormone therapy, agents \_\_\_\_\_

Yes  No

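### The ACUTE block of the follow-up form has no row for urinary retention or obstruction, none for rectal irritation beyond diarrhea and no free row, so non-serious graded acute GU and GI events are likely to be under-recorded

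*Combined protocol and SAP*

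**What the plan says.** Section 2.0 sets out to evaluate acute as well as late toxicity rates, and 2.2.3 lists both among the data to be collected. Section 2.3.2 is narrower on the endpoint, "Secondary endpoint will be late toxicity rate", but its sub-item covers both periods: "Grading of acute and late complications is defined in" Appendix III. Section 10.3 asks for adverse events to be reported with CTC grades from that appendix.

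The second item numbered 10.3.2 gives examples of anticipated acute events. The urinary example is "Urinary irritative or obstructive symptoms – dysuria, increased urinary frequency, nocturia, weak stream, hesitancy, and possible urinary retention". The bowel example is "Rectal irritation – loose stools, cramping, straining, hemorrhoidal inflammation".

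Appendix VIII holds the form on which graded events are entered. Its ACUTE block has ten rows, three of them urinary or bowel: diarrhea, "Urinary frequency/urgency" and dysuria. The others are fatigue, weight loss, alopecia, radiation dermatitis, musculoskeletal pain, and motor and sensory neuropathy. There is no free row. Appendix III does grade urinary retention from 1 to 5; grade 1 begins with "Hesitancy or dribbling, no significant residual urine".

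**The concern.** The protocol names a group of acute symptoms and asks for CTCAE grades, and for retention it supplies the scale. The form that collects the grades then has no line for them. A pre-printed tick-box form steers what gets recorded: an event with no row tends to go unentered, or to be noted without a grade.

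The resulting error runs in one direction, because missing rows can only lower the recorded acute GU and GI rates. Hypothesis 2.1.1 speaks of acceptable complication rates. The series summarised in Section 1.0 are reported as graded acute rates by organ system, for example 42% grade 2 GU and 11% grade 2 GI among 38 patients. Setting rates from this form beside such figures would tend to flatter the present study.

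**Working it through.** No sample size, power or alpha figure bears on this point, and the plan states no figure to reproduce. The check compares three lists: the acute urinary and rectal symptoms in 10.3, the ACUTE rows of Appendix VIII, and the scales in Appendix III. AUA (Appendix IV) and EPIC (Appendix V) are added as parallel sources.

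| Symptom in 10.3 | ACUTE row | Appendix III scale | AUA/EPIC item |
|---|---|---|---|
| Dysuria | Dysuria | Within cystitis, grade 2 | EPIC 3, 6b |
| Frequency | Frequency/urgency | Frequency/urgency | AUA 2, EPIC 6f |
| Nocturia | Frequency/urgency | Frequency/urgency, grade 1 | AUA 7, EPIC 6e |
| Weak stream | None | Not named; nearest is retention | AUA 5, EPIC 6d |
| Hesitancy | None | Urinary retention, grades 1-2 | AUA 6 (nearest) |
| Retention | None | Urinary retention, grades 1-5 | AUA 1, EPIC 6d (incomplete emptying) |
| Loose stools | Diarrhea | Diarrhea | EPIC 10, 15c |
| Cramping | None | Not named; enteritis grade 2 mentions abdominal pain | EPIC 14, 15f |
| Straining (bowel) | None | None | No direct item |
| Hemorrhoidal inflammation | None | None | No direct item |

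**Count.** Urinary: 3 of 6 have a row. Rectal: 1 of 4. Together 3 + 1 = 4 of 10 have a row and 10 - 4 = 6 do not. AUA or EPIC has a direct or close item for 4 of those 6. The LATE block does not fill the gap: its nearest urinary entry is GU stricture, and it has no free row either.

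**What the gap does to a rate.** Take the proportion of patients whose worst acute GU grade is 2 or higher. Then

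recorded rate = true rate - U,

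where U is the proportion of patients whose only grade 2 or higher GU events fall under terms without a row and are not entered elsewhere. A patient with grade 1 frequency and grade 2 hesitancy would be recorded as grade 1 and belongs in U. A patient with grade 2 frequency and grade 2 hesitancy is still recorded as grade 2 and does not. U cannot be negative, so the direction of the bias is fixed. The documents give neither U nor the split of acute GU or GI events by symptom, so its size is not.

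**The case against.** Much can be said for the form as it stands, and most of it limits the point without removing it.

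- **Both organ systems are partly captured.** Frequency/urgency (including nocturia), dysuria and diarrhea all have rows, and grade 3 frequency/urgency in Appendix III includes the need for a catheter. A reader might infer that the form cannot register acute GU or GI toxicity at all. The documents do not support that.
- **AUA and EPIC sit under Toxicity in 10.3.1** and are scheduled at baseline and at five suggested visits after treatment. They cover most of the missing symptoms, but as patient reports without a CTCAE grade, so they cannot supply a graded rate.
- **Serious cases have their own route** through item 5 of the form and 10.3.4. Non-serious cases do not.
- **Nothing confines grading to the printed rows.** This is true, so under-recording is likely rather than certain. The Comments column, however, belongs to the named rows.
- **The list in 10.3 is one of examples.** The count of six out of ten therefore describes the gap but does not show a breach of a specification. For the same reason, the neuropathy rows, which the list does not mention, are not an error.
- **Acute toxicity is not a formal endpoint.** Section 2.3.2 names late toxicity, Section 11.5 plans only the incidence of serious adverse events, and 2.1.1 sets no threshold. No stated decision would change, which keeps the severity low.

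One practical difficulty also stands. Grade 2 retention in Appendix III includes hesitancy that requires medication, while 8.1.4 lists tamsulosin from the first treatment day for at least 3 months as optional premedication. Grades at 6 weeks and 3 months will be hard to read unless the reason for the drug is recorded.

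**Conclusion.** The gap is real and minor. Used as printed, the form is likely to under-record non-serious acute retention or obstruction and rectal irritation other than diarrhea. The graded acute GU and GI rates that serve the objective in 2.0 would then be too low. This assumes that graded acute rates will be compiled from the rows of Appendix VIII, the only form in the documents with a place for acute CTCAE grades.

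The size of the bias cannot be estimated. A reader might be tempted to take the 42% from the cited series and reduce it by an assumed obstructive share. The documents give no such share, and the multiplication would treat obstructive and irritative events as never occurring in the same patient. The late toxicity endpoint and the planned incidence of serious adverse events are not affected by the missing ACUTE rows.

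**What to change.** 1. In the ACUTE block of Appendix VIII, add three rows: urinary retention/obstruction, graded by the existing Appendix III scale; rectal irritation/proctitis; and other, specify.
2. Add a rectal irritation/proctitis grading row to Appendix III, taken from the CTCAE version already used there (v3.0). The appendix has no proctitis, tenesmus or hemorrhoid term, so a new form row alone would have no scale behind it.
3. State in Section 11.5 that acute GU and acute GI toxicity are each reported as the patient's maximum grade over the rows of that organ system.
4. On the retention row, record whether any urinary medication was given as premedication or for symptoms, so that grade 2 can be interpreted.

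The cost is a few form lines, one appendix row and one sentence of analysis text, at visits already planned. Data entry becomes slightly longer and the acute rate may look less favourable. The change is worth making before more visits accrue, because a grade not assigned at the visit may not be recoverable reliably later.

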#### **10.4 Patient Withdrawal from Study**

During the course of the study, it is possible that patients may withdraw or be withdrawn from the study. Factors that may lead to a withdrawal from the study may include, but are not limited to the following:

- Patient Withdrawal.....At any time a patient may voluntarily withdraw from the study. This withdrawal will not affect their future medical treatment or benefits.
- Patient Lost to Follow-Up.....Should a patient be classified as lost to follow-up, efforts to contact the patient should be made.
- Physician Decision.....Should a physician decide that continuing in the study is detrimental to the health and welfare of the patient, the patient may be withdrawn from the study.
- Medical Reason.....Should the patient condition deteriorate the patient may be withdrawn from the study to allow for proper medical care.

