### **11.5 Statistical Analysis**

**11.5.1** The overall survival and biochemical control rates will be analyzed.

**11.5.2** The incidence rate for any serious adverse events will be calculated.

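### Section 10.4 permits withdrawal from the study for deterioration and no visible text keeps follow-up going, so survival, late toxicity and, less so, biochemical control could look better than they are

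*Combined protocol and SAP*

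**What the plan says.** Section 10.4 of the combined protocol and SAP lists four reasons for leaving the study. Two depend on the patient's health. One reads "Should the patient condition deteriorate the patient may be withdrawn from the study to allow for proper medical care". The other applies in this case: "Should a physician decide that continuing in the study is detrimental to the health and welfare of the patient". Both are optional, and both end participation in the study as a whole. For loss to follow-up the section says only "Should a patient be classified as lost to follow-up, efforts to contact the patient should be made". It does not say what data are collected after any kind of withdrawal.

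On outcomes, section 2.3 states "Primary endpoints will be biochemical control rate" and names late toxicity as the secondary endpoint. Section 10.2.1 gives the event as "Biochemical failure defined as nadir + 2 ng/ml" and the PSA schedule as "Will be obtained every 3 months for the first 2 years, then as indicated at the discretion of the treating physician".

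The efficacy analysis in section 11.5 is one sentence: "The overall survival and biochemical control rates will be analyzed". It names no estimator, analysis set, censoring rule or handling of missing data.

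Section 2.2 describes a single-site, non-randomized study expected to run 5 years, with follow-up data taken at routine office visits.

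**The concern.** A patient withdrawn because he is getting worse is not a random loss. Deterioration often precedes death. Several of the late events anticipated in section 10.3.3, such as perforation, bowel obstruction and secondary malignancy, can themselves cause it. If observation stops at that point and the patient is then censored or left out, the patients who remain have a better outlook than those who were treated.

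The direction matters in this design. Section 2.1.2 hypothesises biochemical control at least as good as with standard fractionation, and there is no concurrent arm in which similar losses could offset the effect. Any error of this kind favours the hypothesis. Data not collected after withdrawal may be impossible to recover later, and statistical adjustment would rest on assumptions that the data cannot test.

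**Working it through.** The plan gives no sample size, target rate, margin or expected withdrawal rate, so there is no figure to reproduce. The check has three steps.

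**1. What does withdrawal end?** Section 7.2.1 gives monotherapy as 4–5 fractions and the boost as 2–3 fractions, at 2 to 3 per week. The longest SBRT course is about 5 / 2 = 2.5 weeks. Boost patients also have 25 pelvic fractions. Against an expected 5 years, almost all the time at risk falls after treatment, when being in the study consists mainly of having data recorded. A withdrawal in that period mainly ends follow-up.

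**2. How large could the effect be?** Inputs:
- S, true control. Section 1.0 cites 77.7% at 3 years (high-risk patients given an SBRT boost) and 90% at 4 years (low-risk patients). These come from cited studies and are not design assumptions of this trial.
- w, the share of would-be failures withdrawn just before their event. This is **assumed**: 0, 10%, 25%, 50%.

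If these patients are censored, the observed hazard is (1 − w) times the true hazard, so the Kaplan-Meier estimate tends to S^(1 − w). If they are dropped from a simple proportion, the apparent rate is S / (1 − w(1 − S)).

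| True S | Handling | w = 0 | w = 10% | w = 25% | w = 50% |
|---|---|---|---|---|---|
| 77.7% | censored | 77.7% | 79.7% | 82.8% | 88.1% |
| 77.7% | dropped | 77.7% | 79.5% | 82.3% | 87.5% |
| 90% | censored | 90.0% | 91.0% | 92.4% | 94.9% |
| 90% | dropped | 90.0% | 90.9% | 92.3% | 94.7% |

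Examples: 0.777^0.75 = 0.828, and 0.777 / (1 − 0.25 × 0.223) = 0.777 / 0.94425 = 0.823.

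A simulation of 200,000 patients, with withdrawal 0 to 6 months before failure, gave 79.7%, 82.6% and 88.1% for S = 77.7%, and 90.9%, 92.4% and 94.8% for S = 90%. This agrees with the censoring formula.

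**3. When is there no effect on biochemical control?** The same simulation was run with withdrawal after a recorded PSA failure, and with withdrawal unrelated to failure. Estimates were 77.7–77.8% for a true 77.7% and 89.9–90.0% for a true 90%, so there is no bias in either case.

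No separate calculation was made for overall survival or late toxicity. For those the argument concerns direction only.

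**The case against.** A reader might infer that deteriorating patients do leave the risk set and that the reported rates are therefore overstated. The documents do not support that. Section 11.5 defines no risk set or censoring rule, and section 10.4 does not say that data collection stops. Continued chart follow-up would give no bias, and counting withdrawn patients as failures could bias the rates downward.

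Other text also weakens the worst case. The follow-up form in Appendix VIII has dated fields for recurrence, for further treatment and for death with its cause, so data beyond recurrence are expected. Section 10.3.2 asks for all serious adverse events to be recorded. The sample consent form (Appendix I) is not in the public text and may address data use after withdrawal. For the primary endpoint, PSA is due every 3 months for 2 years, so many failures would be recorded before clinical decline. Zubrod 0–3 is eligible, so decline may have causes unrelated to the cancer.

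These points limit the claim but do not remove it. Nothing visible says that the form is completed, or that serious events are still recorded, after withdrawal. PSA testing is discretionary after year 2, when a failure could go unrecorded. That the clause says may is little comfort, because discretionary removal on grounds of prognosis is still selective.

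Two further inferences go too far. One is that leaving the study can never affect care: section 9.3 bars chemotherapy during SBRT, so withdrawal during treatment could. The other is that no analysis could help: bounds, or weighting on recorded PSA history, would address part of the problem.

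**Conclusion.** The point holds in conditional form. Section 10.4 permits withdrawal from the study for reasons tied to outcome, and no visible text requires follow-up afterwards or says how such patients are analysed. If they are censored or dropped, overall survival is most clearly exposed, late toxicity also, and biochemical control less so.

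The size for this trial is unknown. In the illustration, over w from 0 to 50%, biochemical control is overstated by 0 to 10.4 points when the truth is 77.7% (88.1 − 77.7), and by 0 to 4.9 points when it is 90% (94.9 − 90.0). These figures rest on the assumed w, on withdrawal occurring before the event is recorded, and on withdrawn patients being censored. They are not a forecast. The amendment is worth making because it is cheap and protects data that may not be recoverable later.

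**What to change.** Amend section 10.4 so that deterioration or a physician's decision may end study procedures but does not end follow-up. PSA, toxicity, recurrence and vital status should still be collected, from routine visits or the chart, unless the patient withdraws consent for use of his data. This leaves decisions about clinical care as they are.

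In section 11.5, state that all treated patients stay in the analysis and specify the censoring rule in advance. Report the number of early ends of follow-up and the reason for each. Add a sensitivity analysis that counts withdrawals for deterioration as failures. It serves as a pessimistic bound, not as an estimate.

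The cost is a paragraph in the protocol, slightly more chart follow-up and one extra analysis. Appendix VIII already has fields for PSA, adverse events, recurrence and death.
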